6.2 Anticipated adverse device effects

The only anticipated adverse device effect is the feeling of nasal itching and irritation while initiating the treatment with the medical device Healsea® Children. In case of such adverse reaction, the parents/legal guardians/patients will be instructed to contact the investigator if the patient wishes to stop the nasal spray use.

Version: **2.0; 08 Sep 2021** Page **26** of **61**

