8.1.4 Secondary Endpoints

- **Duration of cold symptoms** (items 2 to 7) will be assessed by means of the WURSS-K (assessed once daily in the evening).

During treatment period, the WURSS-K will be assessed once daily in the evening, taking in account the symptoms from the morning to the evening.

After D10, the WURSS-K will be assessed once daily until the subject feels not sick for two consecutive days.

For each item, the duration is defined as the number of symptomatic days between D1 and the first day the subject reports not having the symptom for two consecutive days.

To be noticed that the duration may be censored at day 30.

- Number of subjects who develop respiratory complication requiring antibiotic prescription during a 20-day follow-up period. Healsea® Children is expected to reduce acute rhinitis complications.
- Frequency and number of days of use of concomitant treatments that may affect common cold symptoms (antibiotics, antipyretics, mucolytics, decongestants, antitussives, systemic and topical

Version: **2.0**; **08** Sep **2021** Page **30** of **61** Study Number: **LPH-2101**

corticosteroids). By reducing duration of common cold symptoms, Healsea® Children will very likely reduce the use of common rescue medication.

- Number of family members in close contact developing common cold symptoms after the patient all over the study period. The daily use of Healsea® Children started at the onset of common cold symptoms is expected to reduce relative's contamination.
- Safety: Assessment of adverse events/incidents/undesirable expected side effects throughout the study.

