4. SAMPLE SIZE

An arbitrary cohort of 200 children has been chosen. A cohort of 100-exposed and 100-not exposed patients is anticipated to allow to demonstrate the interest of using Healsea® Children in the allergic paediatric population.

Indeed, 100 patients by arms are enough to detect a Cohen's effect size of 0.4 with a power of 80% and a type I error of 5%. Cohen's effect size is defined as the standardized difference between AUC in groups. Following Cohen's methodology, 0.4 is an intermediate size between a small effect (0.2) and a medium effect (0.5) and is coherent with the expected result.

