6.3. Statistical/Analytical issues

6.3.1. Significance level

All statistical analyses will be performed at the 0.05 global significance level (type I error rate), using two-sided tests.

The statistical results are conclusive for the primary efficacy criterion.

All the other statistical results have to be considered within a descriptive perspective and not as inferential issues. No adjustment for Type I error is done. P-values of statistical tests will be provided for information only.

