10.2.2. Impact of the treatment chosen on the cold symptoms' duration

Hereinafter, the “recovery date” is the first day of two last days the patient answered to the WURSS-K questionnaire. The patient must have reported a negative answer to the question 1 (“not sick”) and the two last days must be consecutive. Otherwise, there is no “recovery date” for the patient.

For the items 2 to 7 of WURSS-K questionnaire, the duration of the corresponding symptom is defined as the duration between first symptomatic day and last symptomatic day.

Cold symptom's duration (days) = Last symptomatic day – first symptomatic day + 1

For a given symptom, a symptomatic day is a day the patient gave an answer other than negative to the corresponding question (“do not have this”). Missing answers will be imputed by the last observation carried forward (LOCF).

The considered symptomatic days are between D1 and either D30, or the end of the study, or the day before the recovery date, whichever occurs first. Symptomatic days from the recovery date will not be taken into account.

For each of the items 2 to 7 of the WURSS-K questionnaire, the origin date will be the date of the first symptomatic day.

The considered event is the end of the symptom.

For patients who reported a negative answer to the corresponding question on the last day they answered to it, or for patients with a recovery date, the event date will be the last symptomatic day before his/her last day of completion of the questionnaire, or before the recovery date if it exists.

Patients who did not report a negative answer to the corresponding question on the last day they answered to it, and without recovery date, will be censored at D30 or at the end of the study, and the censoring date will be the date of D30 or the reference end date, whichever occurs first.

For patients who never reported the presence of a given symptom (never ticked “a little bad”, “bad” or “very bad”), if they completed the questionnaire at D1, then their origin date will be D1, they will be censored at D1 and their corresponding duration will be zero, else they will have neither origin date nor censoring date and the corresponding duration will be missing.

For each of the items 2 to 7 of the WURSS-K questionnaire, the impact of the treatment chosen on the corresponding cold symptom' duration will be analysed by means of a Cox model. Subjects will be analysed on the FAS.

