12. CHANGES IN THE CONDUCT OF THE STUDY OR PLANNED ANALYSIS

The cold symptoms' duration was defined in the protocol as the number of symptomatic days between D1 and the first day the subject reports not having the symptom for two consecutive days.

Since several patients still reported having symptoms while they reported they did not feel sick anymore at the question 1 during the two last days of completion of the WURSS-K questionnaire, their positive answers to the cold symptoms' items have been considered as non-significant. Consequently, the question 1 has been taken into account instead of the corresponding items to determine the end of the cold symptoms' duration, however only on the condition that the two last days of completion were consecutive.

If the two last days of completion were not consecutive, positive answers to cold symptoms' items are still considered as symptomatic, even if the two last answers to the question 1 are negative. The symptom ends at the last symptomatic day if the patient reported the absence of this symptom after this day. Otherwise, the duration of the symptom is censored at D30 or at the end of the study, whichever occurs first.

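### Symptom-duration Cox models start each item's clock at its first symptomatic day, not D1, so the children analysed depend on onset after treatment starts; SAP 12 does not list the change

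*SAP*

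**What the plan says.** Protocol 8.1.4 opens the count for every item at D1: "the duration is defined as the number of symptomatic days between D1 and the first day the subject reports not having the symptom". Absence has to be reported on two days in a row. The spray is started after Visit 1, which is also D1 (Protocol 8.2).

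SAP 10.2.2 defines duration as the last symptomatic day minus the first symptomatic day plus one. For the Cox model of each of items 2 to 7, "the origin date will be the date of the first symptomatic day". That day may fall anywhere from D1 to D30, the end of the study or the day before recovery. A child who never reports the symptom but completed the D1 diary gets duration zero and is censored at D1.

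SAP 12 repeats the protocol's D1 definition and then justifies a different end: "the question 1 has been taken into account instead of the corresponding items to determine the end of the cold symptoms' duration". It does not mention the different start.

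On status, SAP 6.3.1 says of everything except the primary criterion: "All the other statistical results have to be considered within a descriptive perspective and not as inferential issues".

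**The concern.** Entry requires only one of sore throat, runny nose or blocked nose, within 48 hours of onset and with a total score of at most 9 (Protocol 8.3.1.1). Sneezing, cough or tiredness may be absent on D1 and appear later. Under the SAP rule such a late symptom enters the model at full length. A child in whom it never appears contributes nothing, because a time censored at zero is never in a Cox risk set. The set analysed for each item is therefore the children who ever had the symptom, and treatment can influence that.

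Two distortions are possible. If the spray prevented short late symptoms, those quick recoveries would be missing from the Healsea group only, and a benefit would look like slower recovery. If the spray provoked brief symptoms, the Healsea group would gain quick recoveries. Neither says how long a cold symptom lasts. Symptom duration is the first secondary objective listed, and mock Table 14.2.2.2 gives a hazard ratio and p-value for each item.

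**Working it through.** **1. The plan's own figure.** The documents give no event count, hazard ratio or power for symptom duration. The only stated figure is for the primary AUC: "100 patients by arms are enough to detect a Cohen's effect size of 0.4 with a power of 80% and a type I error of" (the value given there is 5%). With two-sided alpha 0.05, n per group = 2 × (1.960 + 0.842)² / 0.4² = 98.1, rounded up to 99. Power at 100 per group is 80.7% by the normal approximation and 80.4% by the noncentral t. The figure reproduces and this point does not affect it.

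**2. The two definitions side by side, for one item such as sneezing.**

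| Diary | Protocol 8.1.4, as written | SAP 10.2.2 |
|---|---|---|
| Present D1–D7, then absent | 7 days | 7 − 1 + 1 = 7 days, event |
| Absent D1–D4, present D5–D6, then absent | 0 days (rule already met on D1 and D2) | 6 − 5 + 1 = 2 days, event |
| Never present, D1 diary completed | 0 days | 0, censored at D1, in no risk set |

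The first row shows that the origins agree for a child with the symptom on D1. The difference lies entirely in rows two and three.

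**3. Time-zero censoring.** In a simulated data set the Cox hazard ratio was 0.893 both with and without the children censored at zero.

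**4. Possible size.** All rates are assumptions, since the documents give none. There are 100 children per group, symptoms present on D1 last a mean of 7 days, treatment has no effect on the length of any cold symptom, and the Cox model contains treatment only. A hazard ratio below 1 means slower recovery on Healsea. The shift is ln(HR)/0.166, where 0.166 is the typical simulated standard error for the all-onset set.

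| Assumption | All-onset HR | Shift |
|---|---|---|
| 60% present at D1; late symptom (mean 3.5 days) in 25% Healsea vs 50% comparator of the rest | 0.95 | 0.051/0.166 = 0.31 SE |
| Same, 10% vs 50% | 0.90 | 0.105/0.166 = 0.63 SE |
| 50% present at D1; late symptom (mean 3 days) in 20% vs 60% | 0.86 | 0.151/0.166 = 0.91 SE |
| One-day symptom caused in 20% of symptom-free Healsea children | 1.08 | 0.077/0.166 = 0.46 SE |
| Same, 40% | 1.16 | 0.148/0.166 = 0.89 SE |

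Restricted to children with the symptom on D1, the hazard ratio was 1.00–1.02 in these cases. In the three prevention rows Healsea children had roughly 0.3 to 0.6 fewer symptomatic days each, so the hazard ratio pointed the wrong way.

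**5. A second set of assumptions** (late symptoms of mean 2 days; 10%, 30% or 50% absent at D1). Preventing half of late symptoms at random gave 0.98, 0.93 and 0.90. Doubling a 30% late rate gave 1.08 and 1.11 with 30% and 50% absent. Where rejection was simulated at 100 per group, it was 8.5% to 12% under the SAP rule and 3% to 6.5% in D1-present children (400 runs each; Monte Carlo error about 1 to 1.5 points).

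**6. When nothing happens.** With equal late onset in both groups the all-onset hazard ratio was 1.00. With late symptoms as long as early ones it was 0.995 in the first setting and 1.01 in the second. Adjusting for presence at D1 brought the prevention rows of step 4 back to 1.00–1.02. It did not do so when only short symptoms (two days or less) were prevented: in the second setting the adjusted values were 0.93 to 0.96.

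**The case against.** The strongest reply is that the clock is not the cause. For a child symptomatic on D1 both origins coincide, so what matters is which children enter the model. That is right, and the point is framed accordingly.

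Second, SAP 10.2 offers baseline symptom scores as covariates, and in the prevention scenarios adjustment for D1 presence largely removes the shift when prevention is unrelated to duration. This stands in part. The scores enter by stepwise selection at 0.20, a 0–3 score is not the same as presence, Visit 1 does not score tiredness, and adjustment does not cure the caused-symptom case.

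Third, mock Table 14.2.2.2 prints mean duration by group above the hazard ratio, and the zeros that SAP 10.2.2 assigns would show prevented symptoms there. This also stands: only the hazard-ratio line misleads. It does mean that two lines of one table could point in opposite directions.

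Fourth, late symptoms may belong to the same cold, so leaving them out narrows the objective. That is a reason to keep the all-onset model and add to it rather than replace it.

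A reader might also infer that the spray is known to provoke sneezing or a runny nose. The documents do not say so. Protocol 6.2 states: "The only anticipated adverse device effect is the feeling of nasal itching and irritation while initiating the treatment". Neither itching nor irritation is among items 2 to 7, and an effect at initiation could fall on D1, where the origin makes no difference. The caused-symptom rows are therefore an illustration.

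**Conclusion.** The discrepancy is plain from the text. The protocol counts from D1, the SAP counts from each item's first symptomatic day, and SAP 12 declares only the change to the end. As a result, membership of each item's Cox model depends on onset after treatment starts.

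The numerical consequence is conditional and modest. It requires both a treatment difference in late onset and late episodes shorter than early ones. On assumed rates the hazard ratio then moved to about 0.86–0.95 or 1.08–1.16, always by less than one standard error. The share of items absent at D1 is not given, so the real size is unknown.

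Three stronger readings are not supported. The documents do not show that the planned hazard ratios will be biased, or in which direction. The primary conclusion is not at risk, because the AUC does not use this definition. The omission from SAP 12 does not show that the origin was chosen to favour the product; it is an incomplete change list. Because these results are descriptive, the rejection rates carry little weight, but the hazard ratios still need a clear meaning. The change is worth making because it is cheap and uses data already collected.

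**What to change.** - In SAP 10.2.2, add for each of items 2 to 7 a Cox model with origin D1, in children whose D1 diary answer shows the symptom present. All six items can be handled this way, and in this set the two origins coincide.
- As a sensitivity set for the five items also scored at Visit 1 (runny nose, blocked nose, sneezing, sore throat, cough), use a physician score of at least 1. If the D1 and D2 diaries are both negative, assign duration 0 as in Protocol 8.1.4, and state that this counts as an ended symptom and not as censored.
- Report symptoms that first appear after D1 as number and percentage by group, with a risk difference. Interpret the all-onset hazard ratio only alongside this and the D1-present model.
- List the change of origin in SAP 12, with its reason.

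The cost is SAP wording, one more model and one descriptive row per item. No new data are needed. The D1-present model is less precise: its simulated standard error is about 0.185 against 0.166, and 0.185/0.166 = 1.11, so 11% wider. The D1 diary is completed in the evening and may follow a first spray, so presence at D1 is not strictly a pre-treatment measure. The Visit 1 set addresses this for five items but not for tiredness.

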8.1.3 Primary Endpoint

The primary endpoint is the area under the curve (AUC) of the Wisconsin Upper Respiratory Symptom Survey for Kids (WURSS-K) during first 10 days of symptoms. AUC will be calculated applying the trapezoidal rule, with the y-axis, defined by daily WURSS-K scores, and the x-axis, defined as duration of illness, starting with the first symptoms and ending at day 10.

WURSS-K is a 3-dimensional structure questionnaire specifically designed for children 4 to 10 years of age [18] (appendix B). This survey has been demonstrated to be responsible, reliable, and valid for assessing illness specific symptoms and impact on quality of life during an acute infectious rhinitis in paediatric population.

It includes 6 items assessing symptoms (symptoms score: runny nose, stuffy nose, sneezing, sore throat, cough, feeling tired), 7 items assessing functional impairments (quality of life score: think, sleep, breathe, talk, walk/climb stairs/exercise, go to school, play with friends), 1 item assessing global severity. All these items are scored using visual representation of happy and sad faces to assist Likert scale ratings from 0 (absent or no impairment) through 1 (a little bad), 2 (bad) and 3 (very bad). The sum of the 14 items on a 4-point ordinal scale results in a global total score ranging from 0 (low symptoms and low functional impairment) to 42 (high symptoms and high functional impairment). One item assessing global change as compared to the day before is rated from 0 (a lot better) to 4 (a lot worse) is not included in the overall score.

Using an electronic diary, the patient will score the WURSS-K daily in the evening, taking in account the symptoms from the morning to the evening, during D1-D10. After D10, the WURSS-K will be assessed once daily until the subject feels not sick for two consecutive days.

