 incidents/expected undesirable side effects, concomitant medications, and contamination of
 relatives in the e-diary. The legal guardians will access the e-diary website
 (https://me.vieodoc.net) using a smartphone and logging in with a randomly assigned
 username and Pin code. Data recorded in the e-diary will be at the same time uploaded in the
 e-CRF.

D1-D10 (at home):

The patients will be asked to complete the electronic diary daily (WURSS-K assessed once daily in the evening, taking in account the symptoms from the morning to the evening, adverse events/incidents/expected undesirable side effects and concomitant medications, contamination of relatives) and to report Healsea® Children intake if applicable. For the Healsea® Children treated-group, compliance will be indirectly assessed by the question: "do you use the nasal spray as

Version: **2.0**; **08** Sep **2021** Page **35** of **61** Study Number: **LPH-2101**

recommended (1 puff 2 sec in each nostril twice a day)?". If necessary, the parent(s) will help their child in this task.

D5 (Day 5±2, at home): Telephone call 1

The Investigator or his/her delegated designee will call the patient to review patient status and study progress, adverse event/incidents/expected undesirable side effects and concomitant treatments.

Visit 2 (V2) - (Day 10±2): end of treatment

The investigator or his/her delegated designee will:

- Perform a physical and clinical examination,
- Record the common cold symptoms if they persist,
- Validate the adverse events/incidents/expected undesirable side effects and concomitant medications reported in the e-CRF through the e-diary and report any new relevant safety event.

For patients receiving Healsea® children, the treatment will be stopped at D10. The patients for whom common cold symptoms persist, will be instructed to continue to score the WURSS-K until the subject feels not sick for two consecutive days.

D11-D30 (at home):

After D10, the WURSS-K will be assessed once daily until the subject feels not sick for two consecutive days if applicable. The patients will be asked to complete the electronic diary daily (WURSS-K if applicable, adverse events, concomitant medications, and contamination of relatives). If necessary, the parent(s) will help their child in this task.

D20 (Day 20±2, at home): Telephone call 2

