6.4. General conventions and calculated variables**6.4.1. Subject reference start/end dates**

For each subject, the reference dates will be the following:

- The reference start date is the date of inclusion visit.
- The reference end date is the date when subject was determined to have ended the trial.

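### Symptom duration: if a child's diary stops while an item is still positive, SAP 10.2.2 censors at D30 or trial end, so unanswered days count as symptomatic days at risk

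*SAP*

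**What the plan says.** For each of WURSS-K items 2 to 7, SAP 10.2.2 defines a symptom duration and fits a Cox model on the Full Analysis Set. A child has an event if the last answer to the item is negative, or if there is a recovery date. A recovery date needs the last two completed diary days to be consecutive and both marked *not sick*; it is the first of the two. A child with neither is censored, and "the censoring date will be the date of D30 or the reference end date, whichever occurs first". SAP 6.4.1 ties that date to the trial: "The reference end date is the date when subject was determined to have ended the trial". SAP section 12 repeats the rule: "Otherwise, the duration of the symptom is censored at D30 or at the end of the study, whichever occurs first". It adds that when the last two completed days are not consecutive, a ticked symptom still counts, "even if the two last answers to the question 1 are negative".

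Missing item answers are filled by LOCF, and the window is wide: "The considered symptomatic days are between D1 and either D30, or the end of the study, or the day before the recovery date", whichever comes first. On diary length, Protocol 8.1.3 says: "After D10, the WURSS-K will be assessed once daily until the subject feels not sick for two consecutive days". Protocol 8.1.4 says only that a duration may be censored at day 30; it has no rule for a diary that stops sooner. SAP 6.3.1 treats every result other than the primary as descriptive.

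**The concern.** A censoring time should be the last time at which the child was known to be still at risk. Here it can fall weeks after the last answer. From that answer to D30 or trial end, the child stays in the risk set with no chance of an observed event. In effect the symptom is assumed to persist.

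Duration of each symptom is the first secondary objective and feeds six Cox models. If both groups stop equally and there is no true effect, no false difference arises, but a true HR is diluted. If one group stops more often, its symptoms appear to last longer, which favours the group that keeps the diary better. Treatment is open label and chosen by the family, so unequal diary-keeping is plausible.

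**Working it through.** **Plan's own figure.** None exists for this endpoint. The stated 100 per group concerns the primary AUC and reproduces: 2 × (1.96 + 0.84)² / 0.4² ≈ 98 to 99 per group, with power 80.4% at 100 (exact t-test). This point does not affect it.

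**One child.** Duration = last day − first day + 1 (SAP 6.4.2). The symptom starts on D1, the last answer is positive on D8, and there is no recovery date.
- Censored at the last answer: 8 − 1 + 1 = 8 days.
- SAP rule, trial end at D30 or later: 30 − 1 + 1 = 30 days, so 30 − 8 = 22 days have no answer.
- SAP rule, V3 held at D25 (window D30±5): 25 days, so 17 have no answer.

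**Non-consecutive case.** A child is *not sick* on D8 and D10, D9 is missing, and runny nose is ticked throughout.
- No entry after D10: no recovery date, so censored at D30 or trial end.
- D9 also answered *not sick*: recovery date D9, event at D8.
- D9 missing but D11 answered *not sick*: recovery date D10, event at D9.

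The first result therefore arises only if the diary also ends at D10.

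**Share of children affected (rates assumed).** Let p be the daily chance that the symptom ends and s the daily chance that the diary stops for good. An event needs an entry on the day after the last symptomatic day, so P(event) = p(1−s) / [1 − (1−p)(1−s)]. With p = 1/6 (mean 6 days):
- s = 5%: 0.1583 / 0.2083 = 0.76, so 24% are censored.
- s = 2.5%: 0.1625 / 0.1875 = 0.867, so 13% are censored (14% in simulation, which includes symptoms lasting past D30).

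Stopped before D10: 1 − 0.95⁹ = 37% and 1 − 0.975⁹ = 20%.

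**Simulated HR.** Assumptions: 100 per group (both groups in the FAS, as in the mock tables), geometric duration with mean 6 days, trial end uniform on D25 to D35, 1,200 to 1,500 trials per row. In the restart rows, half of stopped diaries resume at each of D5, D10 and D20. With unequal stopping, HR above 1 means faster resolution in the group that stops less.

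| Assumed stopping per day | True HR | SAP rule | Last-answer censoring |
|---|---|---|---|
| 5% vs 2.5%, permanent | 1.0 | 1.25 | 1.03 |
| 2% vs 1%, permanent | 1.0 | 1.13 | 1.01 |
| 1% vs 0.5%, permanent | 1.0 | 1.09 | 1.02 |
| 5% vs 2.5%, restarts | 1.0 | 1.10 | 1.06 |
| 2% vs 1%, restarts | 1.0 | 1.05 | 1.03 |
| 5% both, permanent | 1.0 | 1.00 | 1.00 |
| 5% both, permanent | 1.4 | 1.26 | 1.40 |
| 5% both, restarts | 1.4 | 1.30 | 1.34 |

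A different stopping model gives the same pattern. It assumes exponential durations with median 7 days and a fixed share of diaries stopping between D5 and D14. Stopping of 30% vs 10% gives 1.18 (SAP) against 0.99 (last answer), and 20% vs 10% gives 1.07 against 1.00.

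**Mean duration.** If LOCF runs to D30 or trial end, permanent stopping at 5% vs 2.5% gives means of 10.5 vs 8.4 days, where the truth is 6.0 in both groups. With restarts the means are 7.5 vs 6.8.

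**Limits of last-answer censoring (no true effect).**
- 20% vs 10% of families stop on recovery without a negative entry: SAP 1.30, last-answer 1.13.
- 25% of children recover slowly (mean 18 days, the rest 4) and only they stop. At 10% vs 5% per day: SAP about 1.07, last-answer about 0.95. At 20% vs 5%: about 1.15 and 0.88.

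**The case against.** **The size may be small.** A reader might take 1.25 as the bias to expect. The documents do not support that. They give no stopping rate, and 1.25 needs 37% vs 20% of diaries to end for good before D10. The plan has a call at D5±2, a diary review at V2 and a call at D20±2, and at V2 children with persisting symptoms "will be instructed to continue to score the WURSS-K until the subject feels not sick for two consecutive days". Restarts are therefore plausible, and with them the two rules differ by only 0.02 to 0.04 in HR. This stands.

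**The alternative is not neutral.** Last-answer censoring assumes that stopping is unrelated to remaining duration. When slow-recovering children stop, it is biased about as much as the SAP rule, in the opposite direction. This stands, and is why both analyses should be reported.

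**Duration against Cox time.** A reader might infer that the D8 child's tabulated duration is 8 days while the Cox time is 30, or that the mean difference could reverse. That needs LOCF to stop at the last entry, which SAP 10.2.2 does not say. Read with its window, LOCF most naturally carries the positive answer to D30 or study end, so duration and Cox time agree. The fault is that both include unanswered days.

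**Other safeguards.** A diary with no entry at D10±1 appears to be a major deviation (SAP 7.2), but that removes the child only from the Per-Protocol Set, and this model uses the FAS. Protocol 8.1.4 allows censoring at day 30, which fits a child still answering then; it does not make unanswered days observed. Persisting symptoms are recorded at V2 and V3 (Protocol 8.3.11), but the SAP does not use those records here.

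**Conclusion.** The concern holds as a fault in the rule as written: for a diary that ends early on a positive answer, the censoring date does not follow the last observation. With no true effect, the false HR is about 1.1 for permanent stopping at 2% vs 1% per day, 1.25 at the extreme 5% vs 2.5%, and 1.05 to 1.10 with restarts. Equal stopping leaves a null HR at 1.00 and dilutes a true one. All these sizes rest on assumed rates and, for a false effect, on an assumed imbalance between groups. Children with a negative last answer or a recovery date are untouched, and children who leave the trial near their last entry are little affected. The harm is limited to a misleading descriptive HR and mean duration for a secondary endpoint. The change is worth considering and does not bear on the primary conclusion.

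**What to change.** - Censor each item at the last day it was answered, capped at D30.
- State that LOCF fills gaps between entries only and does not run past the last one.
- Keep the D30/trial-end rule as a reported sensitivity analysis, because either rule can be biased when stopping depends on recovery or on persistent symptoms.
- Tabulate the last-entry day by group.
- Add Kaplan-Meier medians to mock Table 14.2.2.2, and say how censored children enter the mean.
- Where a diary stopped early, compare it with the symptom records at V2 and V3.
- Log the change in SAP section 12, which shows that patients' answers had already been seen when the duration definition was revised.

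Cost: a few lines of SAP text, one extra Cox run for each of the six items, one extra table and the comparison with visit records. No new data are needed.
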